6.4 Transfer

6.4.1 Blastocyst Transfer

Transfer is performed on day 5 (blastocyst stage) after oocyte retrieval. Transfer of day 6 (or later) blastocysts is not allowed. The subject-related procedures are described below.

^b In case the investigator judges that a blastocyst/morula is still developing, cryopreservation on day 6 or later is allowed.

OR: Oocyte retrieval; ICSI: intracytoplasmic sperm injection

Supersedes: 5.0 Page 54 of 103

- Blood collection for central laboratory analysis of anti-MENOPUR antibodies (first post-dosing assessment)
- Ultrasound for image acquisition of the uterus (applicable for a subset of trial sites)
- Ultrasound-guided transfer of blastocyst(s) of the highest quality available according to this policy:

Subjects with at least one good-quality blastocyst (i.e. grade 3BB or above):

> single blastocyst transfer

Subjects with absence of a good-quality blastocyst (i.e. lower than grade 3BB):

- option of single blastocyst transfer
- option of double blastocyst transfer if at least two blastocysts are available

Note: in the absence of viable blastocysts, morulae can be used if deemed suitable for transfer.

- Cryopreservation of blastocysts by vitrification, as applicable
- Dispensing of progesterone for luteal phase support, if applicable
- Recording of use of any concomitant medication
- Recording of adverse events

For subjects with blastocyst transfer, the next visit is the β hCG test visit which must be scheduled 10-14 days after transfer.

6.4.2 First Post-dosing Anti-MENOPUR Antibody Assessment (7-10 Days after Last IMP Dose)

Subjects who have been exposed to MENOPUR liquid or MENOPUR powder must have the first post-dosing anti-MENOPUR antibody assessment performed 7-10 days after the last MENOPUR liquid or MENOPUR powder dose. This may coincide with the transfer visit (section 6.4.1).

For subjects who do not attend the transfer visit, a separate visit must be scheduled, at which the following must take place:

- Blood collection for central laboratory analysis of anti-MENOPUR antibodies
- Recording of use of any concomitant medication
- Recording of adverse events

Date: 14 Oct 2019 E-Study Protocol-21539; Ver. 6.0 Supersedes: 5.0 Page 55 of 103

6.5 βhCG Test

6.5.1 βhCG Test

Subjects who have undergone transfer must attend a visit 10-14 days after transfer.

The following must take place:

- Blood collection for local laboratory analysis of βhCG
- Blood collection for central laboratory analysis of anti-MENOPUR antibodies (second post-dosing assessment (section 6.5.2))
- Dispensing of progesterone, if applicable
- Recording of use of any concomitant medication
- Recording of adverse events

The blood sample for β hCG will be analyzed by the local laboratory and evaluated according to the local reference ranges. In case of doubtful / inconclusive β hCG result, a second test will be performed, preferably within 2 days. Subjects with a positive β hCG test must attend a clinical pregnancy visit 5-6 weeks after transfer (section 6.6). Subjects with a negative β hCG test must proceed to the end-of-trial assessments (section 6.8).

6.5.2 Second Post-dosing Anti-MENOPUR Antibody Assessment (21-28 Days after Last IMP Dose)

Subjects who have been exposed to MENOPUR liquid or MENOPUR powder must have the second post-dosing anti-MENOPUR antibody assessment performed 21-28 days after the last MENOPUR liquid or MENOPUR powder dose. This may coincide with the βhCG visit (section 6.5.1).

For subjects who do not attend the β hCG test visit, a separate visit must be scheduled, at which the following must take place:

- Blood collection for central laboratory analysis of anti-MENOPUR antibodies
- Recording of use of any concomitant medication
- Recording of adverse events

For subjects who do not attend the β hCG test visit, this second post-dosing anti-MENOPUR antibody assessment may be done in connection with the end-of-trial visit (section 6.8).

6.6 Clinical Pregnancy

Subjects with a positive βhCG test must attend a visit 5-6 weeks after transfer.

Date: 14 Oct 2019 E-Study Protocol-21539; Ver. 6.0 Supersedes: 5.0 Page 56 of 103

The following must take place:

- Transvaginal ultrasound of uterus to assess any clinical pregnancy
- Dispensing of progesterone for luteal phase support if a vital pregnancy is confirmed
- Recording of use of any concomitant medication
- Recording of adverse events

If at least one intrauterine gestational sac with fetal heart beat is observed, vital pregnancy is confirmed. For subjects with a vital pregnancy, the next visit is the ongoing pregnancy visit (section 6.7). Subjects with no vital pregnancy must undergo end-of-trial assessments (section 6.8).

6.7 Ongoing Pregnancy

If a vital pregnancy has been documented, the subject must attend a visit 8-9 weeks after transfer.

The following procedures / assessments must take place:

- Ultrasound (transvaginal or abdominal) of uterus to assess any intrauterine viable fetus
- Recording of use of any concomitant medication
- Recording of adverse events

If at least one intrauterine viable fetus is identified, this confirms an ongoing pregnancy.

6.8 End-of-trial

If a subject attends the scheduled trial visits, the end-of-trial assessments should take place at the last scheduled trial visit.

Due to the timing of the mandatory anti-MENOPUR antibody assessments, the end-of-trial assessments can at the earliest be performed 21-28 days after the last MENOPUR liquid or MENOPUR powder dose. This may coincide with the β hCG visit for subjects with a negative β hCG test.

The following end-of-trial procedures / assessments must take place, irrespective of whether the subject discontinues the trial prematurely or completes it:

- Blood collection for central laboratory analysis of:
 - Clinical chemistry and hematology parameters
 - Endocrine parameters (AMH)

Trial Code: 000303

Date: 14 Oct 2019
E-Study Protocol-21539; Ver. 6.0
Supersedes: 5.0
Page 57 of 103

- anti-MENOPUR antibodies (second post-dosing assessment) [note: only applicable for subjects who have not already had a blood sample taken for the second post-dosing anti-MENOPUR antibodies assessment as described in section 6.5.2]
- Vital signs
- Physical examination (including weight)
- Gynecological examination
- Drug accountability, if applicable
- Recording of use of any concomitant medication
- Recording of adverse events
- End-of-trial form (completion of trial or premature discontinuation, date and reason for discontinuation, if applicable)

These assessments serve to document the subject's physical health at the end of the trial.

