2.2 Endpoints

Primary Endpoint

• Number of fertilized (2 pronuclei [2PN]) oocytes at 19±2 hours after insemination.

Secondary Endpoints

- Positive βhCG rate (positive βhCG test 10-14 days after blastocyst transfer).
- Clinical pregnancy rate (transvaginal ultrasound showing at least 1 intrauterine gestational sac with fetal heart beat 5-6 weeks after blastocyst transfer).
- Ongoing pregnancy rate (at least one intrauterine viable fetus 8-9 weeks after blastocyst transfer).
- Early pregnancy loss (defined as a positive βhCG test but no ongoing pregnancy at 8-9 weeks after blastocyst transfer).
- Follicular development as assessed by transvaginal ultrasound on stimulation day 6 and last day of stimulation.

- Endocrine profile:
 - Serum follicle-stimulating hormone (FSH) on day 6, last day of stimulation and at oocyte retrieval, and corresponding population pharmacokinetics (PK) analysis.
 - Serum Anti-Müllerian hormone (AMH) on last day of stimulation and at end-of-trial.
 - Human chorionic gonadotropin (hCG) and luteinizing hormone (LH) on day 6 and last day of stimulation.
 - Estradiol (E2) and progesterone (P4) on day 6 and last day of stimulation.
- Number of oocytes retrieved, number of metaphase II oocytes, fertilization rate, and number and quality of blastocysts 5 days after oocyte retrieval.
- Total gonadotropin dose and number of stimulation days.
- Frequency of OHSS (early OHSS if the onset is ≤9 days after triggering of final follicular maturation and late OHSS if the onset is >9 days after triggering of final follicular maturation).
- Frequency and intensity of adverse events.
- Changes in circulating levels of clinical chemistry and hematology parameters and proportion of subjects with markedly abnormal changes.
- Frequency and intensity of injection site reactions (redness, pain, itching, swelling and bruising) assessed by the subject during the stimulation period.
- Frequency of treatment-induced anti-MENOPUR antibodies, overall as well as with neutralizing capacity.
- Technical malfunctions of the pen.

Post-trial Endpoints

- Live birth rate.
- Late pregnancy loss rate (defined as an ongoing pregnancy but no live birth).
- Neonatal health including SAEs at birth, and SAEs at 4 weeks and minimum 6 months after birth.

Date: 14 Oct 2019 E-Study Protocol-21539; Ver. 6.0 Supersedes: 5.0

[figure not shown]
Page 26 of 103

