Concomitant medication	X ^m	X	X	X	X	X	X	X	X	X	X
Adverse events	X	X	X	X	X	X	X	X	X	X	X
End-of-trial form	Famus ad at the	auhiaat'a la									X

- a) End-of-trial assessments will be performed at the subject's last scheduled visit or the following day or within 2 weeks after the last scheduled visit in the case of premature discontinuation from the trial.
- b) Performed before randomization.
 c) All subjects with a treatment-induced antibody response must be followed until the response is negative or has returned to pre-dosing level.
 d) Sample exclusively used to re-establish the anti-drug antibody analytical assays.
- e) Performed before the first IMP dose.
- f) Blood sampling for antibody assessment must be done 7-10 days after the last IMP dose (this may coincide with the transfer visit; alternatively, a separate visit must be scheduled).
- g) Blood sampling for antibody assessment must be done 21-28 days after the last IMP dose (this may coincide with the \(\beta \) KCG visit; alternatively, a

- g) Blood sampling for antibody assessment must be done 21-28 days after the last IMP dose (this may coincide with the phCG visit; alternatively, separate visit must be scheduled).
 h) Endocrine parameters for analysis by central laboratory: AMH, FSH, hCG, LH, E2 and P4. Special considerations for certain visits are as follows: Screening AMH only, day 1 no E2, day 6 no AMH, oocyte retrieval FSH only, end-of- trial AMH only.
 i) Endocrine parameters for analysis by local laboratory: E2 and P4, optional assessment; performed as per the site's standard practice.
 j) Serum E2 ≤20 pg/mL (central laboratory) and transvaginal ultrasound showing no ovarian cysts.
 k) The gonadotropin starting dose is 225 IU for the first 5 days, followed by individual adjustments according to the subject's follicular response. Dose adjustment should be 75 IU per adjustment. Gonadotropin is to be initiated within 3 days of confirmed downregulation.
 l) Transvaginal ultrasound with exception of the transfer and ongoing pregnancy visits, where it can be either transvaginal or abdominal
- Transvaginal ultrasound with exception of the transfer and ongoing pregnancy visits, where it can be either transvaginal or abdominal examination.
- m) Recording of any concomitant medication within the last 3 months prior to informed consent.

Supersedes: 5.0 Page 47 of 103

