6.2.4 End-of-stimulation Visit

The end-of-stimulation visit takes place when the subject reaches the criterion for triggering of final follicular maturation or if the cycle is cancelled. Administration of hCG (NOVAREL) must take place as soon as reaching the criterion for triggering of final follicular maturation. Should the subject not reach triggering criteria after a maximum of 20 days of stimulation, the end-of-stimulation visit is to occur.

Criterion for triggering of final follicular maturation with hCG:

• 3 follicles of >17 mm

Criterion for cancellation of the cycle due to excessive ovarian response:

• >30 follicles of ≥ 12 mm each and/or E2 levels ≥ 5000 pg/mL (local laboratory)

The following must take place at the end-of-stimulation visit:

- Vital signs
- Transvaginal ultrasound of uterus and ovaries (number and size of follicles)
- Blood collection for central laboratory analysis of:
 - Clinical chemistry and hematology parameters
 - Endocrine parameters (AMH, FSH, hCG, LH, E2 and P4)
- Blood collection for local laboratory analysis of [*note*: optional assessment; performed as per the site's standard practice]:
 - Endocrine parameters (E2 and P4)
- Dispensing of hCG (NOVAREL) (applicable to subjects reaching criterion for triggering only)
- Collection of injection site reaction data (diary pages)
- Drug accountability of IMP and GnRH agonist
- Recording of use of any concomitant medication
- Recording of adverse events

For subjects with hCG administration, the oocyte retrieval visit must be scheduled 36±2 hours after the administration of hCG. Subjects will self-inject hCG (NOVAREL) at home.

Supersedes: 5.0 Page 52 of 103

For subjects with cycle cancellation, a visit for the first post-dosing anti-MENOPUR antibody assessment 7-10 days after the last IMP dose must be scheduled.

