9.3.5 Levels of Endocrine Parameters

The levels of endocrine parameters will be presented by treatment group for both the scheduled visit and the change from baseline for post-baseline visits. Baseline values for endocrine parameters are calculated as defined in Section 1.1.1. Values below the lower limit of quantification (LLOQ) will be included as LLOQ/2. Values above the upper limit of quantification (ULOQ) will be included as ULOQ.

The following list describes which post-baseline visits (and, consequently, change from baseline calculations) are summarized for each of the endocrine parameters.

- AMH: End-of-stimulation and end-of-trial.
- FSH: Stimulation day 6, end-of-stimulation, and oocyte retrieval.
- hCG, LH, Estradiol, and Progesterone: Stimulation day 6 and end-of-stimulation.

For each parameter the change from baseline will be compared between treatment groups using a log-normal model. In this model, the follow-up measurement will be the dependent variable and the linear predictors will include treatment, age strata, and center as factors as well as the baseline measurement (log-transformed) as a covariate. Inferential results will be presented as described in Section 1.2.2.

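### End-of-trial AMH has no defined time point: the sample falls anywhere from about day 21 to day 71 after the last dose, depending on pregnancy outcome

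*Protocol*

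**What the plan says.** Protocol 2.2 and SAP 2.2 list as a secondary endpoint "Serum Anti-Müllerian hormone (AMH) on last day of stimulation and at end-of-trial". SAP 9.3.5 gives the analysis: "For each parameter the change from baseline will be compared between treatment groups using a log-normal model". The model terms are treatment, age strata, center and log baseline.

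The timing of the second AMH sample comes from Protocol 6.8: "If a subject attends the scheduled trial visits, the end-of-trial assessments should take place at the last scheduled trial visit". Table 6-1, footnote a, agrees: "End-of-trial assessments will be performed at the subject's last scheduled visit or the following day". Section 6.8 also sets a floor, because end-of-trial assessments "can at the earliest be performed 21-28 days after the last MENOPUR liquid or MENOPUR powder dose".

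Which visit is last depends on outcome:

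- Negative βhCG (6.5.1), or no transfer: end-of-trial follows, subject to the floor.
- Positive βhCG but no vital pregnancy (6.6): end-of-trial at the clinical pregnancy visit, 5-6 weeks after transfer.
- Vital pregnancy (6.7): "If a vital pregnancy has been documented, the subject must attend a visit 8-9 weeks after transfer".

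Separately, section 6.5.2 says that every exposed woman "must have the second post-dosing anti-MENOPUR antibody assessment performed 21-28 days after the last MENOPUR liquid or MENOPUR powder dose". AMH is taken at that draw only when it happens to be the end-of-trial visit.

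**The concern.** Protocol 3.5.1 commits the trial to standardized assessment timing in order to limit variation. The other post-baseline hormone samples are tied to stimulation day 6, the last day of stimulation or oocyte retrieval. End-of-trial AMH alone is tied to an outcome that arises after randomization.

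The arm means and changes from baseline then describe a mixture of times since stimulation, and of pregnant and non-pregnant women, so they do not estimate AMH at any stated point. If pregnancy rates differ between arms, part of any AMH contrast would reflect that difference. Whether or not they differ, the mixing can add between-subject variance.

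**Working it through.** **Check 1: sampling day.** The documents give no day-since-last-dose figure for the later visits, so it has to be built up.

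Inputs:

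- Last dose to trigger: 0-1 day. This is an assumption; 6.2.4 says only "Administration of hCG (NOVAREL) must take place as soon as reaching the criterion for triggering of final follicular maturation".
- Trigger to retrieval: 36±2 hours, or 1.42-1.58 days (6.3).
- Retrieval to transfer: 5 days (6.4.1).
- Visits after transfer: βhCG 10-14 days, clinical 35-42 days, ongoing 56-63 days (6.5.1, 6.6, 6.7).

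Transfer = (0 to 1) + (1.42 to 1.58) + 5 = day 6.4 to 7.6. This is compatible with the plan's own remark that the 7-10 day antibody sample may coincide with transfer.

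| Visit | Sum | Days after last dose |
|---|---|---|
| βhCG | 6.4+10 to 7.6+14 | 16.4 to 21.6 |
| Clinical | 6.4+35 to 7.6+42 | 41.4 to 49.6 |
| Ongoing | 6.4+56 to 7.6+63 | 62.4 to 70.6 |

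With the floor in 6.8, end-of-trial AMH falls at about day 21-28, 41-50 or 62-71. The span is 71 − 21 = 50 days. A 2-day gap to trigger would move the ongoing visit to about day 64-72.

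The βhCG visit, at about day 16-22, reaches the 21-28 day window only at its late end. Section 6.5.1 nevertheless lists the second antibody sample at that visit. The text of 6.5.2 arranges a separate visit only for women who do not attend the βhCG visit, whereas Table 6-1, footnote g, requires one whenever the two do not coincide.

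**Check 2: state at the 21-28 day draw.** Relative to transfer, that draw is at 21 − 7.6 = 13.4 to 28 − 6.4 = 21.6 days. A βhCG-positive woman is already in early pregnancy by then.

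**Check 3: possible size.** The documents contain no AMH course, so every input here is an assumption. Let p be the share sampled late (0.3-0.5), δ the log-AMH gap between late and early samples (0-0.6), σ the residual log SD (0.4-0.6), and Δp the difference between arms in the share sampled late (0-0.10). Two groups are used for simplicity, although there are three sampling times.

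Variance inflation = 1 + p(1−p)δ²/σ²:

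- δ = 0: 1.00
- p 0.3, δ 0.2, σ 0.6: 1 + 0.21×0.04/0.36 = 1.02
- p 0.4, δ 0.4, σ 0.5: 1 + 0.24×0.16/0.25 = 1.15
- p 0.5, δ 0.6, σ 0.4: 1 + 0.25×0.36/0.16 = 1.56

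Shift in the AMH ratio between arms = exp(Δp·δ) − 1:

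- Δp = 0 or δ = 0: nil
- Δp 0.05, δ 0.2: exp(0.01) − 1 = 1.0%
- Δp 0.10, δ 0.6: exp(0.06) − 1 = 6.2%

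The direction follows the sign of the gap, which is unknown. The 1.56 needs all three inputs at their extremes together.

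**The case against.** The strongest reply is that the comparison is still a valid randomized one. Sampling follows the same rule in both arms, the drug substance is the same, and no difference in pregnancy rate is presumed. If rates did differ, the AMH contrast would be a total effect of treatment. A reader might infer from the mixing that the comparison is biased, or that the model wrongly omits pregnancy. The documents support neither: with equal rates the expected shift is nil, and adjusting for pregnancy would condition on a post-randomization outcome. This part of the reply stands. It does not supply the missing time point.

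Second, moving the sample does not give a single physiological state. That is correct (Check 2), so the variance figures, which compare current practice with no mixing at all, overstate what the change would gain.

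Third, the consequence is small. The secondary objective concerns the endocrine profile during stimulation, which the last-day AMH sample serves. Protocol 9.6.3 plans only descriptive summaries, and the SAP attaches no margin or decision rule to AMH. This stands and limits the severity.

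Fourth, end-of-trial chemistry and hematology share the same variable timing. They do, but 6.8 says that its assessments document physical health at exit. That purpose fits safety laboratory tests better than a post-stimulation hormone level compared in a model.

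A reader might also infer that women lost before a late visit have no AMH value. Section 6.8 requires the end-of-trial sample at premature discontinuation too, so the most that can be said is that some may lack one.

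**Conclusion.** The point holds as a matter of definition and timing. End-of-trial AMH is compared between arms without a defined time after stimulation. It is sampled over about 50 days, in three clusters set by pregnancy outcome. The clusters rest on the protocol's visit windows and one assumption, 0-1 day from last dose to trigger; a 2-day gap changes little.

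The numerical effect is not established. It is nil if pregnancy rates are equal or if AMH does not differ between the sampling situations. Under the assumed ranges the shift is 0% to about 6%. The variance inflation is 2% to 56% for log gaps of 0.2 to 0.6 and nil for a zero gap, and these figures are an upper bound on what the fix could recover.

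Late samples should not be equated with pregnancy. Women without a vital pregnancy finish at about day 41-50, and a woman who loses a vital pregnancy before the ongoing visit is sampled late but is no longer pregnant.

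Severity is low. One secondary endpoint is affected; the primary analysis and the sample size are not.

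**What to change.** In Protocol 6.5.2, 6.8, Table 6-1 footnote h and 7.2.10, draw post-stimulation AMH with the mandatory second antibody sample, 21-28 days after the last IMP dose, in all exposed subjects, whichever visit hosts that draw. Define the endpoint at that time in section 2.2 of both documents and in SAP 9.3.5, and carry the change to 7.3.10, where the AMH schedule is repeated. Leave end-of-trial chemistry and hematology where they are.

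Reconcile 6.5.1, 6.5.2 and 6.8 (with Table 6-1 footnote g) on where the 21-28 day blood is taken when the βhCG visit falls before that window.

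The cost is wording plus one tube moved to a draw that is already required, with no added visit or needle. The 50-day span becomes a 7-day window. The downside is losing the late AMH value in women who continue. Pregnancy status at the draw will still differ between women, and the endpoint description should say so.

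If sampling is already complete, the remaining option is a descriptive SAP table of end-of-trial AMH by days since last dose, by arm, without adding pregnancy to the model.

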6.9 Post-trial Activities

6.9.1 Pregnancy Outcome and Neonatal Health Follow-up

Pregnancy outcome will be gathered for all subjects with an ongoing pregnancy. Neonatal health data will also be collected. In addition, data on neonatal SAEs will be collected at 4 weeks and minimum 6 months after birth. These data will be reported separately.

E-Study Protocol-21539; Ver. 6.0 Supersedes: 5.0 Page 58 of 103

Date: 14 Oct 2019

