7.2.3 Ongoing Pregnancy

Ongoing pregnancy will be based on detection of at least 1 intrauterine viable fetus by transvaginal or abdominal ultrasound at 8-9 weeks after blastocyst transfer. For ongoing pregnancies, the number of intrauterine viable fetuses will be recorded.

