7.4 Assessments Related to Post-trial Information

7.4.1 Pregnancy Outcome and Neonatal Health Follow-up

All subjects with an ongoing pregnancy will be followed as part of the post-trial follow-up. Live birth rate and neonatal health data at birth covering gestational age, gender, birth weight and length, and Apgar scores after 1, 5 and 10 minutes will be collected. In addition, data on neonatal SAEs will be collected at 4 weeks and minimum 6 months after birth (see section 8.5.1). These data will be reported separately.

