A separate information and informed consent form is required to collect pregnancy outcome data on the neonate and the investigator will obtain a freely given written consent from the child-custody holders, i.e. the subject and the subject's partner in case of joint custody. The child-custody holders must be given ample time before the consent is obtained. The Informed Consent Documents must be signed and dated by the child-custody holders and the investigator who has provided information to the child-custody holders. Written consent by the child-custody holders regarding collection of pregnancy outcome data on the neonate must be obtained before the subject is randomized and preferably at the time of obtaining written consent by the subject regarding participation in the trial.

The investigator will explain that the child-custody holders are completely free to refuse to consent to this data collection or to withdraw consent at any time, without any consequences and without the need to justify their decision.

The child-custody holders will receive a copy of the Subject Information and their signed and dated Informed Consent Form before any data collection on the neonate.

Supersedes: 5.0 Page 99 of 103

The child-custody holders will be informed that the monitor(s), quality assurance auditor(s) mandated by Ferring, ethics committee representatives or FDA inspector(s), in accordance with applicable regulatory requirements, may review the neonate's source records and data. Data protection will be handled in compliance with national / local regulations.

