Ferring is issuing a temporary halt of recruitment, i.e. a pause of screening and randomization. Ferring is issuing guidance for continued trial conduct and management of subjects already included in the trial. The table below provides guidance for how to manage the subjects according to stage in the trial.

Temporary halt of recruitment	Continued trial conduct for management of subjects already included in the trial
 Pause screening Pause randomization 	Screened subjects (not yet initiated downregulation): downregulation will not be initiated; the screening period will be extended by the approximate duration of this COVID-19 related temporary recruitment halt
	• Subjects in downregulation (not yet randomized): stop downregulation and do not proceed to randomization; these subjects will be allowed to initiate a new downregulation phase when this COVID-19 related temporary recruitment halt is lifted
	Randomized subjects: continue per protocol and document any deviations

In case subjects are prevented from attending scheduled visits, the investigator (or designee) will attempt to contact the subject by phone or other ways to inquire about potential adverse events and changes to concomitant medication.

IMPLICATIONS OF CHANGE:

The implications of these changes to the protocol are summarized below. The actions are considered urgent safety measures due to COVID-19 required to protect subjects against immediate hazard to their health and safety and are therefore implemented immediately.

- Trial sites, regulatory authorities and independent research boards will be informed.
- Subjects will be verbally informed by the investigator of potential changes to the course of action, as applicable for the individual subject. This will be documented in the subject's medical records.

Date: 19 Mar 2020 E-Protocol Amendment-24122; Ver.1.0 Supersedes: None

Page 4 of 4

- Protocol deviations (including deviations to the aspects described in this 'change to
 protocol') should be avoided whenever possible except where necessary to eliminate an
 immediate hazard to the subject. If deviations occur they will be documented as per
 standard practice, with additional specification whether they were related to the COVID-19
 situation.

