9.3.2 Clinical Pregnancy Rate

The clinical pregnancy rate will be presented by treatment group and analyzed using the method described for secondary pregnancy endpoints in Section 9.1.2. Subjects who do not have at least 1 intrauterine gestational sac, confirmed by TVUS, with a fetal heart beat at 5-6 weeks after blastocyst transfer will be counted as not having clinical pregnancy unless a positive ongoing pregnancy outcome is observed later. For example, if the clinical pregnancy assessment is missing, but the ongoing pregnancy outcome is 'positive' then clinical pregnancy will be imputed as 'positive'.

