10.2.3 Early Pregnancy Loss

Early pregnancy loss is defined as a positive β hCG test but no ongoing pregnancy at 8-9 weeks after blastocyst transfer. The early pregnancy loss rate will be presented by treatment group. The denominator for the early pregnancy loss rate consists of those subjects with a positive β hCG.

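### Post-trial pregnancy and neonatal follow-up depends on a single 8-9 week scan, and the plan gives no route for a confirmed clinical pregnancy that misses it

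*Protocol*

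**What the plan says.** **Entry to follow-up.** Protocol 6.9.1: "Pregnancy outcome will be gathered for all subjects with an ongoing pregnancy". Protocol 7.4.1 repeats it: "All subjects with an ongoing pregnancy will be followed as part of the post-trial follow-up". The synopsis, Protocol 3.1.2, 3.5.6 and 8.5.1, and SAP 3.1 use the same condition.

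**What makes a pregnancy ongoing.** Protocol 7.2.3: "Ongoing pregnancy will be based on detection of at least 1 intrauterine viable fetus by transvaginal" or abdominal ultrasound at 8-9 weeks after transfer. Protocol 6.7, which describes that visit, says: "If at least one intrauterine viable fetus is identified, this confirms an ongoing pregnancy".

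**Missing-data rules around this visit.**
- SAP 9.3.1 and 9.3.2 count an unconfirmed βhCG or clinical pregnancy as negative, with back-fill from a later positive. For clinical pregnancy the exception reads "unless a positive ongoing pregnancy outcome is observed later".
- SAP 9.3.3, on ongoing pregnancy, names the analysis method only.
- Protocol 9.6.1 leaves missing values out of percentages unless something else is specified.
- SAP 10.2.3 defines early loss as a positive βhCG "but no ongoing pregnancy at 8-9 weeks" after transfer, with βhCG-positive subjects as denominator.
- SAP 10.1.1, in the same safety section, keeps missing values missing, apart from four adverse-event attributes.
- SAP 11.1 sets live birth to negative when there is no information.

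**Missed visits.** Protocol Summary of Changes #04 provides for them: "In case subjects are prevented from attending scheduled visits, the investigator (or designee) will attempt to contact the subject by phone" or by other means. The stated purpose is to ask about adverse events and concomitant medication.

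**The concern.** The SAP foresees missed visits for the two earlier pregnancy assessments and repairs them from later information. For the 8-9 week assessment the next information would be the pregnancy outcome, but the plan collects that only if the 8-9 week scan was positive. One missed visit thus removes the data that would show what happened.

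Two things are at stake. The first is safety data: an infant conceived after exposure to trial drug leaves the planned collection of neonatal SAEs at birth, 4 weeks and 6 months. The second is consistent endpoints: the same subject can be unclassified for ongoing pregnancy, arguably an event for early loss, and a failure for live birth.

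**Working it through.** The plan states no figure on this point, so there is none to reproduce. The check is to follow one subject through the rules and then size the effect.

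**One subject: βhCG positive, fetal heart beat at 5-6 weeks, no 8-9 week scan**

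| Item | Rule | Result |
|---|---|---|
| Clinical pregnancy | SAP 9.3.2 | Positive |
| Ongoing pregnancy rate | SAP 9.3.3 silent; Protocol 9.6.1 default | Unspecified: dropped from the percentage under the protocol default, negative by analogy with 9.3.1-9.3.2 |
| Early pregnancy loss | SAP 10.2.3 against SAP 10.1.1 | Event on the literal definition, missing under the safety rule |
| Entry to follow-up | Protocol 6.9.1, 7.4.1; SAP 3.1 | No written route |
| Live birth | SAP 11.1 | Negative if nothing is collected |
| Neonatal SAEs | Protocol 8.5.1 | Outside planned collection |

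The one remaining safety route, Protocol 8.6.3, covers only SAEs that the investigator happens to learn of and considers possibly related to trial drug. The neonatal events in Protocol 8.5.1 (for example intensive-care admission or congenital anomaly) are recorded without that filter, but only within post-trial follow-up.

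**Size, on assumed rates**

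From the documents: N = 200 per arm. Assumed, because the documents give none: clinical pregnancy rate p, proportion of these truly ongoing q = 90%, proportion missing the 8-9 week scan m, with missing a scan unrelated to viability.

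- Unclassified per arm = N × p × m.
- Continuing pregnancies not followed per arm = N × p × q × m.
- Ongoing rate if missing is negative = p × q × (1 − m).
- Ongoing rate if missing is dropped = p × q × (1 − m) / (1 − p × m).

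With p = 40%, there are 80 clinical pregnancies and 72 truly ongoing per arm, a true rate of 36.0%:

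| m | Unclassified per arm | Continuing, not followed, per arm | Rate, missing negative | Rate, missing dropped |
|---|---|---|---|---|
| 1% | 0.8 | 0.7 | 35.6% | 35.8% |
| 3% | 2.4 | 2.2 | 34.9% | 35.3% |
| 5% | 4.0 | 3.6 | 34.2% | 34.9% |
| 10% | 8.0 | 7.2 | 32.4% | 33.8% |

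For m between 2% and 5%, continuing pregnancies lost across both arms are 2 × 72 × 0.02 = 2.9 to 2 × 72 × 0.05 = 7.2. Letting p run from 30% to 50% and m from 1% to 10% widens this to between 2 × 200 × 0.3 × 0.9 × 0.01 = 1.1 and 2 × 200 × 0.5 × 0.9 × 0.10 = 18.

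Live birth at p = 40%, m = 5%: if all 3.6 unfollowed pregnancies end in live birth, the rate is understated by 3.6 / 200 = 1.8 points per arm.

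Early loss at p = 40%, m = 5%, assuming 100 positive βhCG tests per arm: the true rate is (100 − 72) / 100 = 28%. The literal definition gives (100 − 68.4) / 100 = 31.6%. Keeping missing as missing gives 20 + 8 × 0.95 = 27.6 losses out of 96, or 28.8%.

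**The case against.** Several points on the other side are sound.

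- **A reader might infer that the missed scan is scored as not ongoing.** The documents do not say so. SAP 9.3.3 is silent, and the protocol default would leave the subject out of the percentage. The negative score is an analogy with the neighbouring sections.
- **A reader might infer that she is counted as an early loss.** The literal definition allows it, but SAP 10.1.1 governs the section that holds this endpoint, and an unperformed assessment is a missing value. Protocol 8.4.4 also starts from a pregnancy loss that has occurred, and its categories need ultrasound, surgery or reported menstruation. What stands is a conflict between rules.
- **A reader might infer that the loss is informative and biases the comparison.** Nothing in the documents suggests that missed scans differ by arm in a double-blind trial. A similar small shortfall in both arms barely moves the difference, and these endpoints carry no non-inferiority margin.
- **Follow-up is not forbidden.** The source-data list in Protocol 10.1 includes pregnancy outcome without an 8-9 week condition, Protocol 3.5.6 allows unscheduled visits, and an adverse-event call could bring a loss to light. A diligent site might collect the outcome anyway. None of these is an instruction to do so, and every description of post-trial follow-up carries the ongoing-pregnancy condition.
- **Back-filling ongoing pregnancy from live birth has a cost.** Under Protocol 13.1 and SAP 11, births are reported later in an addendum, so a main-report endpoint would wait on them. This objection stands, and the fix below avoids it.

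**Conclusion.** The concern holds for follow-up. The condition for entry is a stated rule, repeated consistently, and it leaves a viable clinical pregnancy with a missed 8-9 week scan without a written route into outcome and neonatal collection. Live birth then defaults to negative. For the ongoing pregnancy rate the handling is unspecified, and for early loss two SAP rules disagree. The documents do not support saying that she is definitely scored as not ongoing or as an early loss.

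The effect is probably a handful of subjects: about 3 to 7 continuing pregnancies across the trial at 40% clinical pregnancy, 90% of these ongoing and 2-5% missed. All three rates are assumptions. The primary endpoint is assessed before transfer and is unaffected, and no between-arm bias is shown. The case for change rests on complete neonatal safety data and consistent endpoint rules, at low cost.

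**What to change.** 1. **Protocol 6.9.1 and 7.4.1, and SAP 3.1:** open post-trial follow-up to every subject with a clinical pregnancy and no documented loss. Align the repeats in the synopsis and Protocol 3.1.2, 3.5.6 and 8.5.1.
2. **SAP 9.3.3:** state the missing-data rule in line with 9.3.1-9.3.2, that is, negative unless a later scan shows a viable fetus. Show any reclassification from a live birth only in the post-trial addendum.
3. **SAP 10.2.3:** state that unknown 8-9 week status is not an early loss, and report the number of such subjects separately by treatment group.

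The cost is a few extra outcome contacts. No new consent step is needed before randomization: under Protocol 14.5, written consent of the child-custody holders to collect pregnancy outcome data on the neonate already "must be obtained before the subject is randomized". The wording of that form should be checked so that it covers subjects whose 8-9 week status is unknown. Treatment, the visit schedule and the primary analysis do not change.
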